6.2 Study Procedures and Assessments

6.2.1 Screening Period / Visit -1 (Day -84 to Day 1)

Participants will complete eligibility screening online or by phone. Interested participants will then complete consent online via DocuSign or a paper copy of the consent will be mailed to them with an addressed, prepaid return envelope. The consent documents will include contact information for the study team, in case the potential participants have any questions.

After an individual provides informed consent, the following activities will be performed during the Screening Period:

- Medical record review, if available – age, insurance status, cancer diagnosis, stage, treatments, recurrence, metastases. This will not be required to assess eligibility.
- Inclusion/exclusion criteria review
- Enrollment Surveys:
 - Sociodemographic and clinical variables
 - Dietary Assessment (food frequency questionnaire; FFQ)
 - Food Security module from the National Health Interview Survey
 - Theoretical constructs assessed using a modified Food Beliefs survey
 - Pre-existing adverse events assessed by a Recent Health Survey, using questions from the NCI's Patient Reported Outcomes version of the Common Terminology Criteria for Adverse Events (PRO-CTCAE)

6.2.2 Study Intervention Period (Day 1-84)

- Text message intervention engagement (text message responses)
- Non-response interview (if applicable)

6.2.3 End of Study Intervention (Study Week 12 ± 84 days)

- 12-week surveys:
 - Dietary Assessment (FFQ)
 - Food Security module from the National Health Interview Survey
 - Theoretical constructs assessed using a modified Food Beliefs survey
 - Adverse events in past 12 weeks assessed by a Recent Health Survey, using questions from the NCI's Patient Reported Outcomes version of the Common Terminology Criteria for Adverse Events (PRO-CTCAE). Medical records may be collected in the event that an SAE occurs.
 - System Usability Scale (SUS)
 - Acceptability of Intervention Measure (AIM)

- Intervention Appropriateness Measure (IAM)
- Feasibility of Intervention Measure (FIM)
- End of study interview (optional)

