1.5 Risks/Benefits

Potential Risks

The risks involved in this study are few. There is a minor risk of loss of confidentiality, either through the breach of data collected via the Internet or text messaging or through the breach of secure study databases, physical files, etc. Dietary modifications may result in changes in bowel function, including but not limited to diarrhea, constipation, increased urgency, flatulence, and/or bloating. These changes are not expected to be clinically significant but could impact quality of life if they occur.

Potential Benefit of the Proposed Research to Participants and Others

The benefits of healthy diet are well established. Intervention participants may experience decreases in symptom burden and improved physical functioning and quality of life. This study will produce societal benefit regarding knowledge about how to optimize a text message-based intervention to improve diet quality in cancer survivors. Given the minimal risk of study participation and potential benefits, the risks to participants are reasonable in relation to the anticipated benefits to society.

Procedures used to minimize risk

- Numerous studies have demonstrated that healthy diet is safe, feasible, and beneficial for cancer patients and survivors.
- Participants will receive tips on how to alleviate or avoid digestive changes due to increased whole grain and fiber intake.
- Participants will be asked to contact the study team at any time if they have questions or concerns about the study.

- All study files, folders, and records will be kept in locked file cabinets that can be accessed only by study personnel.
- All data will be exchanged over an SSL-protected connection, and all data will be encrypted.
- The study database and all survey data will be collected and stored in REDCap, the HealthySMS platform, Twilio, and UCSF's Research Analysis Environment (RAE), which have protections needed for storage of PHI.

Limited private identifiable information necessary for the conduct of the study will be collected in the proposed research project. For example: names, phone numbers, and email addresses. This information will be stored securely in REDCap, the HealthySMS platform, Twilio, and UCSF's Research Analysis Environment (RAE; mytransfer.ucsf.edu), which have the protections in place and approvals for the storage of PHI.

Importance of Knowledge to be Gained

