4.6 Assignment to Intervention

This is a single-arm study. All participants will receive the 12-week adaptive text message intervention.

5 Study Intervention

We aim to develop a dietary intervention that will continuously adapt text message content and timing based on factors that may include: participants' sociodemographic characteristics, dietary behavior, and engagement with the text messages.

Our theoretical framework is based on the Capability Opportunity Motivation-Behavior (COM-B) model which states that individuals' behaviors are the result of interactions between their capabilities, opportunities, and motivations. Applying the model to whole grain intake, CRC survivors must have:

- 1) capability – the physical ability to consume whole grains without side effects (e.g., gas, bloating, bowel frequency); knowledge and skills to select and prepare whole grains; and psychological capability to resist cravings and control urges for refined grains;
- 2) opportunity – whole grains must be available, affordable, and socially acceptable; and
- 3) motivation – motivated to eat whole grains and develop a plan for doing so.

Intervention Components

Adaptive text messages using reinforcement learning (RL)

After completing baseline assessments, all participants will receive text messages for 12 weeks. Most days, participants will receive 1-2 messages. Text messages will be sent through the HealthySMS Platform and Twilio. Message content will target COM-B components of capability, opportunities, and motivations. The RL model will use a bank of text messages to target COM-B constructs. For example, to address psychological capability, messages will increase knowledge of what foods are recommended and how to prepare them. Behavior change techniques will include providing information, feedback, self-monitoring, and prompts/cues to increase knowledge. To address physical opportunity, text messages will focus on how to economically shop for and prepare whole grain foods. Behavior change techniques will include restructuring the physical environment, prompts/cues, instruction, feedback, and self-monitoring.

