5.3 Adherence Assessment

Intervention Adherence

Adherence to the intervention will be measured using number of replies to text messages that asked for a response.

Proposed Engagement Strategies for Retention

To prevent attrition, our study staff develop good rapport and open, responsive communication with participants. Participants will be provided with a phone number and email address to contact if they encounter issues with any aspect of the study. Staff will convey reminders of study tasks by phone, email, and/or text messages. Participants may be compensated with gift cards as described in Section 4.2. If a participant does not respond to a study-related request, up to five automated reminders will be sent and the study staff will reach out to the participant

via phone and/or e-mail. If we are unable to reach a participant after three more attempts, we will determine a participant lost to follow-up.

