6.1 Schedule of Activities

Period/Procedure	Screening/Baseline	Study Intervention Period	End of Study
	Visit -1 (D-84 to D1)	Weeks 1-12 (D1 to D84)	Study Week 12 (+/-84 days)
Administrative Procedures			
Consent ¹	X		
Medical Record Review, if available	X ²		
Inclusion/Exclusion Criteria	X		
Other Study Assessments			
Sociodemographic and Clinical Variables survey	X		
Adverse Events (Recent Health Survey) ³	X		X
Dietary Assessment Survey (FFQ)	X		X
Food Security Survey	X		X
Food Beliefs Survey (theoretical constructs)	X		X
Text Message Intervention Engagement ⁴		Throughout	
“Reasons for Non-Response” Interview		See Footnote 6	
System Usability Scale (SUS)			X
Acceptability of Intervention Measure (AIM)			X
Intervention Appropriateness Measure (IAM)			X
Feasibility of Intervention Measure (FIM)			X
End of Study Interview (optional)			X

1 DocuSign or paper copy mail with prepaid return envelope

2 Participants will be allowed to self-report their clinical information if no medical records are available (e.g., patients for whom we cannot obtain records).

3 Pre-existing expected adverse events (e.g., diarrhea, constipation, etc.) will be assessed at enrollment via a Recent Health Survey containing questions from PRO-CTCAE, and emergent events will be assessed at 12 weeks. Medical records may be collected in the event that an SAE is observed.

4 Measured via text message response

5 Food Security module from the National Health Interview Survey

6 Only for participants who do not respond to text messages; If a participant does not respond to text messages for 7 days, we will invite them to a semi-structured interview to understand reasons for non-response.

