8.1 Definition of Adverse Event (AE)

An adverse event (AE) is defined as any untoward medical occurrence associated with the use of an intervention in humans, whether or not considered intervention related.

Adverse event assessment:

A Recent Health Survey with modified questions from the NCI Patient Reported Outcomes version of the Common Terminology Criteria for Adverse Events (PRO-CTCAE) Measurement System will be used to collect AEs by self-report in study participants. The survey measures participant-reported frequency, severity, and interference of expected symptoms and also allows the participant to report the severity of unexpected symptoms. Most symptoms are graded on a 5 point Likert scale ranging from 0 to 4. Frequency responses are assessed by the question "How often do you have [symptom]?" and include: Never, Rarely, Occasionally, Frequently, and Almost constantly. Severity responses are assessed by the question "What was the severity of your [symptom] at its worst?" and include: None, Mild, Moderate, Severe, Very Severe. Interference responses are assessed by "How much did [the symptom] interfere with your usual or daily activities?" and include: Not at all, A little bit, Somewhat, Quite a bit, and Very much. For this study, assessments of frequency, severity, and interference are based on a 12-week recall period.

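### The end-of-study adverse event survey looks back 12 weeks from the day it is answered, not to the first message, so a late survey leaves early intervention days outside recall

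*Combined protocol and SAP*

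**What the plan says.** Section 5 (Intervention Components) states that after baseline "all participants will receive text messages for 12 weeks", and the schedule in section 6.1 places this at Day 1 to Day 84.

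Section 6.2.3 lists, among the 12-week surveys, "Adverse events in past 12 weeks assessed by a Recent Health Survey". Section 8.1 adds that "assessments of frequency, severity, and interference are based on a 12-week recall period". Neither gives a calendar anchor such as the date of the first message.

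The schedule in 6.1 and the heading of 6.2.3 both accept the end-of-study assessments at week 12 plus or minus 84 days. Footnote 3 of the schedule assigns pre-existing symptoms to the enrollment survey and emergent ones to the 12-week survey. No adverse event measure is scheduled in between (6.2.2), and section 6.2.4 plans no follow-up after the intervention.

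The physical risk named in section 1.5 is digestive: "Dietary modifications may result in changes in bowel function". Footnote 3 of the schedule treats diarrhea and constipation as expected events.

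**The concern.** The survey is the only scheduled look at symptoms that arise on the intervention. Its recall period has the same length as the exposure but is fixed to a different date: the exposure starts at the first message, while the recall ends on the day the participant answers. The two periods coincide only for a survey answered on Day 84.

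The plan leaves room for answers on other days. Besides the 84-day tolerance on either side, section 5.3 says that when a request goes unanswered "up to five automated reminders will be sent and the study staff will reach out to the participant", and section 5.5 allows up to three further staff contacts. A participant who answers late is asked about a period that omits the start of messaging. One who answers early is asked about days before messaging began.

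At stake is the completeness of the tolerability record. Bowel symptoms are the expected physical harm, section 8.5 promises follow-up of participants who have adverse events, and section 1.4 says the results will inform a later randomized trial. A symptom outside the recall period is not asked about anywhere else.

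**Working it through.** The plan states no figure for how much of the exposure the survey covers, so there is none to reproduce. The check is an overlap of two intervals.

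**Inputs**
- Exposure: Day 1 to Day 84, 84 days (sections 5 and 6.1).
- Recall: 12 weeks = 84 days, ending on the day of completion (6.2.3 and 8.1, reading the past 12 weeks in the ordinary sense).
- Accepted completion: Day 84 − 84 = Day 0 to Day 84 + 84 = Day 168 (6.1 and 6.2.3).

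**Formulas**
- Answered d days after Day 84: recall runs from Day d + 1 to Day 84 + d. Intervention days covered = 84 − d. The first d intervention days are lost and d post-messaging days enter.
- Answered e days before Day 84: recall runs from Day 1 − e to Day 84 − e. Intervention days covered = 84 − e. Then e pre-intervention days enter, and the last e intervention days have not yet happened.

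| Survey answered | Recall period | Intervention days covered | Days outside the intervention |
|---|---|---|---|
| Day 70 (14 early) | Day −13 to 70 | 70/84 = 83% | 14 before |
| Day 84 | Day 1 to 84 | 84/84 = 100% | 0 |
| Day 98 (14 late) | Day 15 to 98 | 70/84 = 83% | 14 after |
| Day 112 (28 late) | Day 29 to 112 | 56/84 = 67% | 28 after |
| Day 126 (42 late) | Day 43 to 126 | 42/84 = 50% | 42 after |
| Day 168 (84 late) | Day 85 to 168 | 0/84 = 0% | 84 after |

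**From days to symptoms.** Suppose, as an assumption, that a symptom occurs on a single day, equally likely to be any of the 84. The chance that a late survey misses it is d/84; at 28 days late, 28/84 = 33%. If it occurs on two independent days, both must fall in the lost stretch: (28/84)² = 11%. A symptom that persists past Day d, or keeps recurring, is still inside the recall and is reported, although its worst severity could be understated if the peak fell earlier. Under even spread, d/84 is therefore an upper bound on the share of symptoms missed. If symptoms cluster in the lost days the share could be larger, and if they arise later it is smaller.

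**With recall starting at Day 1.** A survey answered on Day 84 + d asks about Day 1 to Day 84 + d. All 84 intervention days are covered at any d ≥ 0, and recall length is 84 + d days: 98 at 14 days late, 112 at 28, 168 at the limit.

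**The case against.** The strongest reply is that the large figures belong to the visit window. Coverage of 50% or 0% arises only because completion is accepted up to 84 days late; under a tighter window, say 14 days, at least 83% of intervention days stay covered. This stands as to size. It does not remove the mismatch, which exists for any survey not answered on Day 84.

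The reminder procedure in 5.3 and 5.5 is generic, gives no intervals and ends in loss to follow-up, so it shows that delay is possible but not how long it is. The survey form is also not in the documents: the question stems in 8.1 carry no recall phrase, and the form might already show a start date. Both points stand.

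Participants may contact the team at any time (section 1.5), and the platform supports two-way messages (5.1). This mitigates the gap in part, but it depends on participants raising the symptom themselves.

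Four stronger readings are tempting, and the documents do not support them:
- *Lost days are lost symptoms.* The items in 8.1 ask about frequency and worst severity, so one qualifying day inside the recall is enough to report a symptom.
- *Early symptoms will be under-counted because diet changes first in the early weeks.* No timing is given. Sections 5 and 9.2.3 have messages sent at random at first and adapted later, so dietary change could as well grow with time.
- *Late responders are the ones with problems.* Nothing in the plan says so.
- *Symptoms after Day 84 are contamination.* Section 1.5 attributes bowel change to diet, which may stay changed after the messages stop.

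**Conclusion.** The point holds as a mismatch between recall and exposure in the only scheduled post-baseline adverse event measure. Following the plan as written can leave part of the intervention outside the question, and at the last accepted day all of it. Expected bowel symptoms confined to the uncovered days would then go unrecorded by any scheduled measure.

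The size of any resulting bias cannot be stated, because the documents give neither the distribution of completion dates nor the timing of symptoms. The tabulated shares describe days. The conclusion also assumes that the survey is worded as 6.2.3 and 8.1 describe it.

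This is a change to consider rather than one the study depends on. Adverse events are not among the primary, secondary or exploratory endpoints in section 2, section 9.2 contains no adverse event analysis, section 8.4 classes the study as minimal risk, and section 1.5 does not expect the bowel changes to be clinically important.

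**What to change.** - In 6.2.3 and 8.1, start the end-of-study recall at the first message, for example: *since you started receiving the study text messages on [start date]*. Set no end cut-off. A cut-off at the last message would discard later symptoms that may be related to diet, and would name a date not yet reached for anyone answering before Day 84.
- Keep the 12-week recall in the baseline survey.
- Record the completion date, and report the recall length and the number of surveys completed before and after Day 84. For early surveys the new anchor removes the pre-intervention days, but the remaining intervention days stay unobserved, so the count is needed.
- Reconcile 6.2.4, which plans no follow-up after the intervention, with a survey accepted up to 84 days later.

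The cost is one wording change in a survey whose items are already modified (8.1) and which runs in REDCap (7.1), where the start date can be filled in, with the same insertion on any paper copies. The downside is a recall longer than 12 weeks for late responders, up to 168 days under the present window, so their period no longer matches baseline and the comparison of pre-existing with emergent symptoms is less even. A narrower visit window would limit this.

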6.2.4 Follow-up

Participants will not be followed after discontinuing the study intervention.

7 Reporting and Documentation of Results

7.1 Measures and Instruments

Dietary Assessment Survey (FFQ)

Participants will complete a validated food frequency questionnaire (FFQ) at enrollment and week 12.³⁰ The FFQ will ask about diet in the past 3 months. For each item, participants will be asked to report how often, on average, they ate the specified portion size in the past 3 months. Participants can choose from frequency options ranging from never or less than once per month to ≥6 times a day. To compute calorie and nutrient intakes, we will multiply the frequency of consumption of each food by the amount of each nutrient in the specified portion size using composition values from the U.S. Department of Agriculture and other sources.

The FFQ specifically queries intake of the following whole grain items: cooked oatmeal/cooked oat bran (including instant); other cooked breakfast cereal, including grits; whole wheat, whole grain oat, whole multigrain bread or pita; whole grain/whole wheat crackers; brown rice; whole grain pasta, e.g., spaghetti, macaroni; other whole grains, e.g., quinoa, barley, spelt, etc. Refined grains on the FFQ include: white, wheat, oatmeal (not whole grain) bread or pita; rye/pumpernickel bread or pita; tortillas; corn or flour, e.g., burritos, quesadillas etc.; other crackers; bagels, English muffins, or rolls; muffins or biscuits; pancakes or waffles; white rice; other pasta (not whole grain), e.g., spaghetti, noodles, macaroni, etc. Participants also report intake of cold breakfast cereal and the brand of cereal that they eat most often; cereal brand is used to classify their cold breakfast cereal intake as whole or refined grain. Using these data, we will calculate the percent of total grains that are whole, servings/day of whole grains and refined grains, and total fiber (g/d) at each time point.

The survey will be administered using REDCap. A paper FFQ will be made available for participants who are not able to complete the survey online.

Other Survey Data

Participants will be asked to complete additional surveys using REDCap at 0 and 12 weeks. Paper copies will be made available for participants who are not able to complete the surveys online.

Sociodemographic and clinical factors will be assessed at baseline.

At baseline and 12 weeks, a Recent Health Survey with questions from the NCI Patient Reported Outcomes version of the Common Terminology Criteria for Adverse Events (PRO-CTCAE) Measurement System will be used to collect adverse events (AEs) by self-report in study participants.

At 0 and 12-weeks, we will use validated surveys to measure theoretical constructs: the Food Security module from the National Health Interview Survey and a modified Food Beliefs survey (which includes self-efficacy, social support, self-monitoring, etc.).

At 12-weeks, we will assess usability and acceptability of the intervention via the System Usability Scale (SUS), Acceptability of Intervention Measure (AIM), Intervention Appropriateness Measure (IAM), and the Feasibility of Intervention Measure.³¹ The System Usability Scale (SUS) is a valid and reliable 10-item tool for measuring usability.³² The acceptability of each intervention component (e.g., behavior change messages, whole grain intake messages, educational material, food security support) will be evaluated separately.

End of study interview (optional)

Participants may be invited to complete an optional 15 to 30-minute end of study interview to obtain open-ended, qualitative feedback.

8 Adverse Events and Serious Adverse Events

8.1 Definition of Adverse Event (AE)

An adverse event (AE) is defined as any untoward medical occurrence associated with the use of an intervention in humans, whether or not considered intervention related.

Adverse event assessment:

A Recent Health Survey with modified questions from the NCI Patient Reported Outcomes version of the Common Terminology Criteria for Adverse Events (PRO-CTCAE) Measurement System will be used to collect AEs by self-report in study participants. The survey measures participant-reported frequency, severity, and interference of expected symptoms and also allows the participant to report the severity of unexpected symptoms. Most symptoms are graded on a 5 point Likert scale ranging from 0 to 4. Frequency responses are assessed by the question "How often do you have [symptom]?" and include: Never, Rarely, Occasionally, Frequently, and Almost constantly. Severity responses are assessed by the question "What was the severity of your [symptom] at its worst?" and include: None, Mild, Moderate, Severe, Very Severe. Interference responses are assessed by "How much did [the symptom] interfere with your usual or daily activities?" and include: Not at all, A little bit, Somewhat, Quite a bit, and Very much. For this study, assessments of frequency, severity, and interference are based on a 12-week recall period.

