8.2 Definition of Serious Adverse Event (SAE)

A participant-reported AE that results in any of the following outcomes is defined as a Serious Adverse Event:

- Death,
- Life-threatening adverse experience*,
- Inpatient hospitalization or prolongation of existing hospitalization,
- Persistent or significant disability/incapacity,
- Congenital anomaly/birth defect, or cancer, or

- Any other experience that suggests a significant hazard, contraindication, side effect or precaution that may require medical or surgical intervention to prevent one of the outcomes listed above,
- Event that changes the risk/benefit ratio of the study.

*A life-threatening adverse experience is any AE that places the patient or participant, in the view of the investigator, at immediate risk of death from the reaction as it occurred, i.e., it does not include a reaction that, had it occurred in a more severe form, might have caused death.

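### As described, the only adverse event survey asks about symptoms and not the outcomes that make an event serious, so SAEs can go undetected unless volunteered or noticed by staff

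*Combined protocol and SAP*

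**What the plan says.** **Instrument.** Section 8.1 says the Recent Health Survey, built on modified PRO-CTCAE questions, "will be used to collect AEs by self-report in study participants". No other AE instrument is named in 6.1, 6.2, 7.1 or 8.

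**Content.** "The survey measures participant-reported frequency, severity, and interference of expected symptoms and also allows the participant to report the severity of unexpected symptoms". Section 8.1 also gives the question stems and response options for frequency, severity and interference.

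**Timing.** The survey is given at enrollment for pre-existing symptoms, and "emergent events will be assessed at 12 weeks" (6.1 footnote 3). The "assessments of frequency, severity, and interference are based on a 12-week recall period" (8.1).

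**SAE definition.** "A participant-reported AE that results in any of the following outcomes is defined as a Serious Adverse Event" (8.2). The list includes "Inpatient hospitalization or prolongation of existing hospitalization" and a line reading "Congenital anomaly/birth defect, or cancer, or", together with death, threat to life, disability and two broader categories.

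**Records.** "Medical records may be collected in the event that an SAE occurs" (6.2.3). Footnote 3 of 6.1 says the same of an SAE that is observed. The only other record review is at screening, where records are available (6.2.1).

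**The concern.** Severity and seriousness are different properties. The survey scale records how bad a symptom felt; 8.2 asks what the event led to. Section 8.3.1 keeps the two apart, using the survey's severity responses for expected non-serious events and CTCAE v5.0 for events judged serious, but it does not say what information supports that judgement. A participant admitted with a bowel problem and one who had the same symptom at home could give identical answers to every item 8.1 describes. A new cancer found on a scan might produce no symptom to report.

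What is at stake is the completeness of SAE ascertainment. Grading (8.3.1), attribution (8.3.2), DSMC review (8.4) and reporting to the IRB (8.6) all begin once an SAE has been recognised, and the plan does not say how recognition happens.

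**Working it through.** The plan states no figure on this point, so there is nothing to reproduce. The check sets the sections side by side.

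**Step 1. Outcomes in 8.2 against items described in 8.1**

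| Outcome in 8.2 | Can a participant report it? | Item described in 8.1 |
|---|---|---|
| Death | No | None |
| Threat to life | Yes | None; the top severity category does not ask this |
| Hospital admission or longer stay | Yes | None |
| Lasting or major disability | Yes | None; interference with daily activities overlaps loosely |
| Cancer | Yes | None |
| Congenital anomaly | In principle | None |
| Other significant hazard; change in risk/benefit | Needs investigator judgement | None |

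The entry for unexpected symptoms could bring an admission to light, but as described it asks for the symptom's severity and not its consequence.

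**Step 2. Other routes by which an SAE could become known**

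- Section 1.5: participants are invited to contact the team with questions or concerns. This is a general invitation, not an SAE instruction.
- Section 5.1: the messaging platform supports two-way communication. No AE query is described.
- Section 5 and 6.1 footnote 6: an interview may follow 7 days without replies. Its purpose is to learn why the participant stopped replying.
- Sections 5.3 and 5.5: staff phone or e-mail people who miss study requests. The purpose is retention.
- Section 7.1: an optional end-of-study interview collects qualitative feedback.
- Section 8.5: participants with AEs are followed until the event settles. This applies only once an AE is known.
- Section 6.2.1: record review takes place at screening, so it cannot show events during the intervention.

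Any of these might reveal an SAE incidentally. None is set up to elicit one.

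**Step 3. The record trigger**

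Both record sentences are permissive and take effect after an SAE is observed or occurs. Records can then document or clarify the event. As a means of detection the trigger is circular, because it needs the fact that the records would supply.

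**Step 4. Participants without a 12-week survey**

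Section 9.1.1 plans for up to 60 participants and 20% drop-out: 60 × 0.20 = 12 without end-of-study data, and 60 − 12 = 48 with it. That drop-out figure belongs to the power calculation for the diet outcome. Assuming the same people also miss the Recent Health Survey, about 12 would have no planned AE collection after baseline.

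**The case against.** **The questionnaire is not in the documents.** Footnote 3 of 6.1 and section 7.1 say the survey contains PRO-CTCAE questions; they do not say it contains nothing else. This objection stands. A reader might infer that participants are certainly never asked about admissions or new cancers. The documents do not support that. They show only that no such item is described, in a section that otherwise sets out stems and response options in detail.

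**Staff would probably hear of many events.** The routes in step 2, the follow-up in 8.5 and the listing of unacceptable AEs as a discontinuation reason in 5.4 all imply some awareness. This stands in part: it would be too strong to say that SAEs come to light by luck alone. But 8.5 concerns medical management of an AE already known, and no route asks about outcomes systematically.

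**The record sentences do not bar other access.** True. They permit collection in one circumstance and do not forbid it in others. Equally, they plan no post-baseline look that could find an event.

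**The study is minimal risk and has no safety endpoint.** This stands and limits the weight. Safety is not among the objectives in section 2, SAEs attributed to the intervention are not expected (8.3.2), and eligible participants are off active treatment and recovered from surgery (4.1.1). A reader might put a number on missed SAEs, or say that a report of none would undermine the later randomized trial. Neither follows: the documents give no rate of admission or new cancer, and no planned conclusion rests on an upper limit for SAEs.

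**Conclusion.** The point holds as a gap in the described ascertainment of SAEs. The AE instrument is described in terms of symptoms, SAEs are defined by outcome, and the one post-baseline use of records depends on an SAE already being known. Under the plan as written, an event that 8.2 calls serious can go undetected unless the participant volunteers it or staff happen to learn of it.

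The conclusion rests on 8.1 being a fair account of the survey. If the form already asks about these outcomes, only the protocol text is deficient. The number of SAEs that might be missed cannot be derived from the documents. The one figure available is the roughly 12 of 60 who might return no 12-week survey, on the assumption stated above. Primary and secondary analyses are unaffected. Because the study is minimal risk, this is a low-priority improvement.

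**What to change.** **Main change (8.1 and 6.2.3).** Add short yes/no items to the 12-week Recent Health Survey for the 8.2 outcomes a participant can report, each with date and reason:

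- inpatient admission or prolonged stay;
- life-threatening event;
- new lasting disability;
- new cancer diagnosis, with recurrence of the colorectal cancer recorded separately, because 8.2 does not say whether recurrence counts.

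Let any positive answer trigger the record request. If such items already exist, a sentence in 8.1 stating them is enough.

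**Optional addition.** Where UCSF or ZSFG records are already accessible, make one chart check at week 12 for participants who do not return the survey. This requires reconciling the participant-reported condition in 8.2, under which a death or an admission found in a chart would not count as an SAE.

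**Cost.** A few minutes per participant, an IRB-approved amendment signed by the PI (10.4), some staff time if the chart check is adopted, and a likely higher count of SAEs, mostly unrelated to the intervention. Admissions to outside hospitals may still be missed, particularly among people who do not return the survey.
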